2.3 Translational endpoints

- To evaluate PD-L1 by IHC and COX-1/COX-2 expression by mRNA in pre- treatment cancer tissues (focusing on epithelial cell expression and immune cell expression).
- To evaluate infiltrating CD3+, CD4+ and CD3+, CD8+ T cells in pre- and post- PD-L1 antibody treated patient cancer tissues by IHC.
- To evaluate change in regulatory B-cell populations with treatment as identified by IHC for CD1d, CD5, CD19 and CD24.
- To evaluate mRNA levels of the following chemokines/cytokines and immune checkpoints on formalin fixed paraffin embedded (FFPE) tissue from pre- and post- treatment specimens: IFN- γ , TNF- α , TNF- β , T-box protein in B-cells (T-bet), IL-2, IL-10, IL-35, FOXP-3, CTLA-4, LAG-3, PD-L1, Granzyme-A and Perforin-1.

[figure not shown]
3. STUDY DESIGN

3.1 Overview of Study Design

This is a pilot study of avelumab in patients with non-metastatic, MIBC who are eligible for RC, but refuse or are ineligible for cisplatin based NAC. The target recruitment is 10 evaluable patients for this window of opportunity study. Pre- and post-treatment tumor samples from TURBT and RC will be used for study endpoints.

Patients will be recruited from sites within the academic system of Baylor College of Medicine. Recruitment will be over one year and patients will undergo systemic treatment followed by surgery as per protocol. They will be followed for 2 years for survival, recurrence, and safety monitoring.

3.2 Study Schema

3.3 Study Oversight for Safety Evaluation

In metastatic UCC, the high grade treatment related adverse event rate with avelumab is approximately 10% and the rate of serious adverse events (SAEs) is 5-10%. (54-59)

Treatment may be put on hold, and pending full review of the data, the study may be stopped if any of the following criteria are met:

- Two (2) avelumab-related SAEs are reported
- At least 2 subjects experience a similar unanticipated avelumab-related AE

3.4 Evaluability and Patient Replacement

Patients will continue to be enrolled on study until we have enrolled/treated 10 patients who are evaluable for the primary endpoint. Patients will be replaced after enrollment if they are later determined not to be evaluable for the primary endpoint.

Evaluable patients

- For primary endpoint
 - Receive \geq 1 dose of avelumab, undergo RC within 5 weeks of last dose of avelumab, and are not started on systemic steroids at a dose of > 10 mg/d of prednisone or equivalent, while taking avelumab.
- For safety endpoint
 - Receive \geq 1 dose of avelumab
- For pathologic complete response/partial response
 - Receive \geq 1 dose of avelumab and undergo RC < 42 days from last avelumab dose
- For 2 year disease free survival
 - Meet evaluability criteria for complete response/partial response, participate in 90 day on study follow-up after RC and participate in off study follow-up as part of regular care up to 2 years post RC.

Inevaluable patients

- Patients who receive < 1 dose of avelumab after study enrollment for any reason.

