5.3 Radical Cystectomy (RC)

- Patients will undergo RC within five weeks after the 3rd dose of avelumab.
- Cystectomy will be done per standard clinical care.

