5.5 Table 5: Adverse Drug Reactions Requiring Avelumab Discontinuation or Modification

Any Grade 4 ADR requires treatment discontinuation with avelumab, except for single laboratory values out of normal range that are unlikely related to study treatment as assessed by the Investigator, do not have any clinical correlate, and resolve within 7 days with adequate medical management.

Any Grade 3 ADR requires treatment discontinuation with avelumab except for any of the following:

- Transient (\leq 6 hours) Grade 3 flu-like symptoms or fever, which is controlled with medical management
- Transient (\leq 24 hours) Grade 3 fatigue, local reactions, headache, nausea, emesis that resolves to Grade \leq 1
- Single laboratory values out of normal range (excluding Grade \geq 3 liver function test increase) that are unlikely related to study treatment according to the Investigator, do not have any clinical correlate, and resolve to Grade \leq 1 within 7 days with adequate medical management
- Tumor flare phenomenon defined as local pain, irritation, or rash localized at sites of known or suspected tumor

- Change in ECOG PS to ≥ 3 that resolves to ≤ 2 within 14 days (infusions should not be given on the following cycle, if the ECOG PS is ≥ 3 on the day of study drug administration)

Any Grade 2 ADR should be managed as follows:

- If a Grade 2 ADR resolves to Grade ≤ 1 by the last day of the current cycle, treatment may continue.
- If a Grade 2 ADR does not resolve to Grade ≤ 1 by the last day of the current cycle, infusions should not be given on the following cycle. If at the end of the following cycle the event has not resolved to Grade 1, the subject should permanently discontinue treatment with avelumab ADR (except for hormone insufficiencies that can be managed by replacement therapy).
- Upon the second occurrence of the same Grade 2 ADR (except for hormone insufficiencies that can be managed by replacement therapy) in the same subject, treatment with avelumab has to be permanently discontinued.

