7. STUDY PROCEDURES

7.1 Study Calendar

Time Points	Pre-study	C1	C2	C3	Pre-surgery ^b	Surgery	Follow-up			End of Study visit	Follow-up
	30 days before D1	D1	D15	D29	D40-50	D41-64	2-3 weeks post-op	30 days post-op	60 days post-op	90 days post-op ^c	To 2 years post-op
Study Assessment											
Signed Informed Consent	X										
Eligibility Criteria	X										
Cancer Staging	X										
Physical Exam with ECOG Performance Status (PS)	X ^a		X	X	X ^b		X	X	X	X ^c	
Medical History/Smoking History/Occupation Hazard	X										
FFPE Tissue for Translational Endpoints^d	X						X				
Laboratory Analysis											
CBC with diff and CMP	X		X	X	X		X	X	X	X	
UPT (if female of CBP)	X			X	X						
Hepatitis B surface antigen, Hepatitis C antibody and HIV 1/2 ELISA	X										
Hepatitis C RNA (if hepatitis C antibody positive)	X										
ACTH, Hemoglobin A1C, and TSH	X				X			X		X	
Free T4 (if TSH abnormal as indicated in Table 7)	X				X			X		X	
Imaging											
CT chest ^e	X				X					X	
CT or MRI abdomen/pelvis ^f	X				X					X	
Treatment											
Avelumab		X	X	X							
Adverse events and their management noted			X	X	X		X	X	X	X ^g	
Radical Cystectomy						X					
Pathology Assessment							X				
DFS Follow-up post-study											X

Footnotes:

- a. Enrollment history and physical.
- b. End of treatment visit.
- c. End of study visit to be performed no earlier than Day 90 after RC.
- d. FFPE tissue from the pre-study time point refers to tissue from the TURBT. FFPE tissue from the 2-3 week post-op time point refers to FFPE tissue from the RC.
- e. Contrast will be used as long as not precluded by creatinine clearance. If a patient is allergic to CT contrast they will be appropriately pre-medicated with steroids +/- antihistamines unless they have a history of anaphylaxis. CT of the chest to be completed in +/- 14 days.
- f. CT with contrast is preferable. However, MRI with contrast or non-contrast CT may be done based on creatinine clearance, allergies, and ability to tolerate contrast. If a patient is allergic to CT contrast, they will be appropriately pre-medicated with steroids +/- antihistamines unless they have a history of anaphylaxis. CT of the abdomen/pelvis to be completed in +/- 14 days.
- g. To be performed at the end of study visit.

Allowable Windows:

1. TURBT should be done within 6 weeks of registration.
2. Avelumab administration should be within +/- 3 days of listed days.

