3. Laboratory analysis on day 15 and day 29 may be performed on the day of infusion if results are received prior to avelumab administration. Alternatively, these laboratory analysis may be performed the day prior to avelumab administration.
4. The **end of treatment visit** (post-treatment pre-surgery) should be performed between days 40 and 50.
5. The **end of study visit** should be 90 days after surgery +/- 10 days.
6. On-treatment visits with history and physical exam should be ≤ 3 days before a scheduled dose of avelumab.
7. RC may be done any time after the pre-surgery evaluation is completed, but no later than day 64.
8. History and physical exams performed after RC (with the exception of the end of study visit) have a time window of +/- 7 days.
9. Post-operative labs up to day 60 after RC have a time window of +/- 7 days.

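### Section 3.4's primary-evaluability rules do not fit the surgical schedule: early stoppers have no matching cystectomy date, and steroids first started between the last dose and cystectomy are not covered

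*Protocol*

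**What the plan says.** For the primary endpoint, Protocol 3.4 requires at least one dose of avelumab, that the patient "undergo RC within 5 weeks of last dose of avelumab", and that patients "are not started on systemic steroids at a dose of > 10 mg/d of prednisone or equivalent, while taking avelumab". Patients who fail these conditions are replaced until 10 are evaluable.

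Surgery is timed elsewhere. Section 5.3 states: "Patients will undergo RC within five weeks after the 3rd dose of avelumab". The 7.1 calendar has three dosing days (D1, D15, D29), a pre-surgery visit on D40-50 and RC on D41-64. Its windows add: "RC may be done any time after the pre-surgery evaluation is completed, but no later than day 64". For dosing: "Avelumab administration should be within +/- 3 days of listed days".

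The protocol expects some patients to stop early. In 5.5, "Any Grade 3 ADR requires treatment discontinuation with avelumab except for any of the following" is followed by a short list of exceptions, and Grade 4 is treated similarly. A Grade 2 reaction leads to a skipped infusion, and "If at the end of the following cycle the event has not resolved to Grade 1", treatment stops for good. Section 4.3 stops avelumab after a delay of more than 2 weeks. It says that such patients still have surgery and that some may count for the primary outcome.

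Table 7 (5.7) treats immune reactions with systemic steroids, usually tapered over at least a month. Section 6.2 permits steroids given for that purpose during the study. The post-treatment sample is RC tissue (3.1, 7.1).

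**The concern.** The primary comparison is TURBT tissue against RC tissue in 10 pairs, so each pair is a tenth of the primary data. Two gaps affect which pairs enter.

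- **Timing.** Section 3.4 counts from the last dose received, whereas 5.3 and 7.1 count from a completed three-dose course. For a patient who stops early, the protocol gives no surgery date consistent with 3.4. A site that keeps to the calendar loses a one-dose patient who could have been evaluable, and that patient is replaced.
- **Steroids.** Section 3.4 treats exposure above 10 mg/d as disqualifying, but ties the rule to the period on avelumab. The tissue it protects is taken later. A course begun after the last dose and still running at RC leaves the pair in the primary set, and no other rule removes it.

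**Working it through.** **The plan's own figure first.** Section 10.1 gives about 80% power for 10 pairs, a 1 SD change, r = 0.5 and two-sided 5%. The standardised paired effect is 1/√(2(1 − 0.5)) = 1.0. A paired t-test with n = 10 (df 9, noncentrality √10 = 3.16) has power 80.3%. The figure is reproduced, and nothing below changes it.

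**Timing.** Inputs: doses on D1, D15 and D29 (5.2), each ±3 days (7.1); limit = last dose + 35 days (3.4); calendar RC days D41-64, which is 24 days (7.1).

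| Doses received | Last dose (with window) | Limit, +35 days | Calendar RC days inside the limit |
|---|---|---|---|
| 1 | D1 (latest D4) | D36 (latest D39) | 0 |
| 2 | D15 (D12-18) | D50 (D47-53) | D41-50, 10 days (7-13) |
| 3 | D29 (D26-32) | D64 (D61-67, capped at D64) | D41-64, 24 days (21-24) |

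After one dose, even surgery on D40, the first permitted day for the pre-surgery visit, is past D39.

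**Is there time to operate sooner after one dose?**

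- Grade 3-4 reaction in cycle 1 (which ends on D14): at least D15-36, 22 days.
- Grade 2 reaction unresolved at the end of the skipped cycle (D28): D29-36, 8 days.
- 4.3 delay rule (dose due D15, more than 14 days late, so D30): D30-36, 7 days.

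Evaluable surgery is therefore possible in calendar terms, but it falls outside the only dates given.

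**Steroids.** After a last dose on D29:

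- Treatment ends at the last infusion: the gap to RC is 41 − 29 = 12 to 64 − 29 = 35 days.
- Treatment ends with cycle 3 (D29 + 13 = D42): the gap is 0 days (RC on D41-42) to 64 − 42 = 22 days.

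The lowest weight-based steroid dose in Table 7 is 0.5 mg/kg/day of methylprednisolone. Taken milligram for milligram, that exceeds 10 mg/d for anyone above 10/0.5 = 20 kg. If a course starts on D30 and lasts only a one-month taper (assumption), it runs to D59 and overlaps D41-59, 19 of the 24 RC days. The dose may be 10 mg/d or less late in the taper.

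**Number affected.** The protocol gives no rate for stopping after one dose or for starting steroids after the last dose, so I give no expected count.

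**The case against.** **The calendar describes a full course.** This is right, and it limits the timing point. Nothing tells a patient who stops after D1 to wait until D40, D64 is only an upper limit, and 3.4 itself supplies the criterion for short courses. A reader might infer that a one-dose patient can never be evaluable. The documents do not support that: earlier surgery is not forbidden, and the patient is lost only if the site applies the three-dose dates. Section 4.3 also says only that some early stoppers may count. What stands is that no text gives an alternative date. I did not have the schema figure in 3.2 and cannot exclude that it shows one.

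**The two gaps overlap.** Many patients who stop early for toxicity will need Table 7 steroids above 10 mg/d and would be excluded whatever their surgery date. This stands. Re-timing surgery helps only early stoppers without disqualifying steroids.

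**The steroid clause already catches the main cases.** A reader might infer that, because Table 7 stops avelumab when systemic steroids are needed, the clause misses those very patients. That is strained: a patient whose steroid start triggers discontinuation is most naturally still taking avelumab at that moment. The gap is confined to courses first started after the last dose.

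**Extending the clause conditions on a post-treatment event.** Immune reactions may track T-cell activation, so removing more of these patients could itself shift a single-arm result. This also stands. It is the reason to show the result both ways.

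**Conclusion.** A minor point, but a sound one. Held to the 7.1 calendar, a one-dose patient has no RC day that satisfies 3.4 and a two-dose patient has 10 of 24, while three doses on the listed days fit exactly. Separately, RC tissue taken on more than 10 mg/d of steroid can enter a 10-pair primary set if the course began after the last dose. The uncovered interval is 12-35 days or 0-22 days, depending on when treatment is taken to end.

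The timing conclusion assumes that the site applies the full-course dates to an early stopper. The steroid conclusion assumes that the clause is applied as worded. Few patients are likely to be affected. Because inevaluable patients are replaced, the target of 10 pairs and the stated power are untouched.

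**What to change.** **Timing (5.3 and 7.1).** Count the pre-surgery visit as 11-21 days, and RC as 12-35 days, after the last avelumab dose actually received, subject to fitness for surgery.

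- Three doses: 29 + 11 = D40 to 29 + 21 = D50 for the visit, and 29 + 12 = D41 to 29 + 35 = D64 for RC, as now.
- Two doses: RC on D27-50.
- One dose: RC on D13-36.
- If the decision to stop comes more than 21 days after the last dose (the Grade 2 and delay rules), hold the visit then and operate by day 35 if feasible; otherwise replace the patient.

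**Steroids (3.4).** Run the clause from the first avelumab dose until RC. Carry over the 4.2a exception for steroid premedication; otherwise contrast premedication for the pre-surgery CT, which the 7.1 footnotes allow, could disqualify a patient. Report the primary result with and without steroid-treated patients.

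**Cost.** One sentence in 5.3, calendar footnotes in 7.1 and one line in 3.4. A few more patients may be excluded and replaced for toxicity managed with steroids, and the two-way report makes that visible.

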1.7 Research Hypotheses

- Primary Hypothesis: Avelumab treatment will result in an increase in CD3+CD4+ T-cell and CD3+CD8+ T-cell infiltrates.
- Secondary Hypotheses:
 - Pathological response rate will be comparable to historical controls receiving NA cisplatin based chemotherapy.
 - 2 year disease free survival (DFS) will be better than historical controls not receiving NAC and comparable to historical controls receiving cisplatin based NAC.
 - Avelumab will be safe and tolerable in our patient population.
 - Infiltration of regulatory B-cells will increase with avelumab treatment and increased levels will be associated with less response to treatment.
 - Increased COX-1 and COX-2 levels on transurethral resection of the bladder tumor (TURBT) tissue will be associated with decreased response to avelumab.

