4.3 Withdrawal of Subjects from Study Treatment and/or Study

An individual subject will not receive any further investigational product if any of the following occur after enrollment on study:

- Withdrawal of consent by subject
- Subject is determined to have met one or more of the exclusion criteria for study participation at study entry and continuing investigational therapy might constitute a safety risk
- Pregnancy or intent to become pregnant
- Any criteria that necessitates discontinuation of study treatment as outlined in sections 5.5-5.7
- Subject noncompliance that in the opinion of the investigator or sponsor warrants withdrawal; e.g., refusal to adhere to scheduled visits
- Initiation of alternative anticancer therapy including another investigational agent
- Subject has > 2 week delay in the administration of avelumab. Such patients will still receive surgery and laboratory/clinical follow-up to complete the 90 day safety monitoring after RC. Some of these patients may be evaluable for primary and/or secondary outcomes.

Subjects who are permanently discontinued from further receipt of avelumab, regardless of the reason, will be identified as having permanently discontinued treatment.

- **Withdrawal of consent**

Patients are free to withdraw their consent to further participation in this trial without prejudice. If consent is withdrawn, the subject will not receive any further investigational product.

- **Withdrawal from study**

Patients determined to be inevaluable will be removed from study. Such patients will receive standard of care and follow-up. Such patients will be followed off study for recurrence and/or survival as part of routine care.

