7.2.5 Follow-up schedule

- Any patient receiving ≥ 1 dose of avelumab will be followed up to 90 days after RC (or end of last cycle of avelumab for those not receiving RC) to evaluate for safety. The indicated follow-up is outlined in the study calendar.
- Those patients evaluable for secondary endpoints will be followed up on study to day 90 after RC as outlined in the study calendar.
- After the safety monitoring period of 90 days post RC those patients who are evaluable for secondary endpoints will be followed off study for recurrence and survival for up to 2 years after RC. This may be done by physician visits/imaging performed approximately every 3 months for those undergoing surveillance at Baylor affiliates or by phone conversations approximately every 3 months for those undergoing surveillance at practices outside of Baylor affiliates.

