10.2 Statistical analysis

To see the change in T cells pre- and post-treatment, paired t-test or nonparametric Wilcoxon signed rank test will be used after checking its normality.

Pathological response rate will be estimated along with 95% confidence interval. Two year disease free survival will be calculated using Kaplan-Meier survival curves with estimates of median and 95% confidence interval. Patients who are decided not to be evaluable for the primary outcome will be considered evaluable for the safety analysis and secondary outcomes, such patients will be summarized descriptively. The correlation of translational studies with response parameters will be summarized descriptively. Changes from pre- and post- treatment will be assessed using paired tests. SAS software will be used for all statistical analyses.

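### Under protocol 3.4, treated patients who never reach cystectomy leave the pathologic response denominator, and 10.2 does not say whether they enter the rate and its 95% CI

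*Protocol*

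**What the plan says.** Section 3.4 sets evaluability endpoint by endpoint. For the primary endpoint a patient needs at least one dose, RC within 5 weeks of the last dose, and no systemic steroids above a stated dose while on avelumab. For pathologic response a patient needs at least one dose and must "undergo RC < 42 days from last avelumab dose". For safety one dose is enough. Section 3.4 also states: "Patients will be replaced after enrollment if they are later determined not to be evaluable for the primary endpoint".

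Section 10.2 plans the analysis in one sentence: "Pathological response rate will be estimated along with 95% confidence interval". It names no denominator. It then says: "Patients who are decided not to be evaluable for the primary outcome will be considered evaluable for the safety analysis and secondary outcomes", and adds that these patients are summarised descriptively.

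Two other sections treat secondary evaluability as conditional. Section 4.3, on patients whose dosing is delayed by more than 2 weeks, says: "Some of these patients may be evaluable for primary and/or secondary outcomes". Section 7.2.5 says: "Those patients evaluable for secondary endpoints will be followed up on study to day 90 after RC".

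Section 7.2.5 also foresees treated patients who have no surgery. It starts their safety follow-up at the "end of last cycle of avelumab for those not receiving RC".

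The use of the rate is given in 1.7: "Pathological response rate will be comparable to historical controls receiving NA cisplatin based chemotherapy".

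**The concern.** Pathologic response is downstaging to below pT2, or complete response (2.2), and the post-treatment tissue comes from RC (3.1). A treated patient who never has RC therefore cannot be recorded as a responder. Under 3.4 that patient is removed from the denominator and is not counted as a non-response. Read literally, 10.2 makes the same patient evaluable for the endpoint. The two sections give different answers, and an analyst could follow either.

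Where 3.4 is followed, the exclusion works in one direction only: it can raise the rate relative to all treated patients but never lower it. The size of the denominator does not reveal the loss, because replacement keeps refilling the evaluable set. The rate is secondary, but 1.7 sets it against outside figures, so a reader needs to know which patients it covers.

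**Working it through.** **No plan figure to reproduce.** The protocol gives no target, sample size or power for the response rate. The power statement in 10.1 concerns the T-cell change and does not bear on this point.

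**Step 1: which section governs.** Some patients fail the primary rule but still satisfy 3.4 for response: those with RC after 5 weeks but before day 42, and those started on steroids above the limit. For them 3.4 and the general sentence in 10.2 agree. For a treated patient with no RC they disagree. Because 4.3 and 7.2.5 make secondary evaluability conditional, 3.4 is the likelier rule. Even so, the descriptive-summary clause in 10.2 does not say whether such patients are inside or outside the rate and its interval.

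**Step 2: size of the 3.4 set.** Enrolment continues until 10 patients are evaluable for the primary endpoint. That requires RC within 5 × 7 = 35 days, which lies inside the limit of fewer than 42 days. At full accrual the 3.4 response set therefore holds at least 10 patients, however many others were treated and had no RC.

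**Step 3: direction.** Let x be the responders and n the patients in the 3.4 set, and let k be the further treated patients without RC.

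- 3.4 rate = x/n
- All-treated rate, no RC counted as non-response = x/(n + k)
- Ratio of the first to the second = (n + k)/n, which is at least 1 and does not depend on x when x > 0

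**Step 4: numbers.** From the protocol: n is at least 10. Assumed, because the protocol gives no figure: n = 10 exactly, x = 3, no late RC, and k from 0 to 4. Intervals are exact (Clopper-Pearson) 95%.

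| k | 3.4 rate | All-treated rate (95% CI) | Ratio |
|---|---|---|---|
| 0 | 30.0% | 3/10 = 30.0% (6.7 to 65.2) | 1.0 |
| 1 | 30.0% | 3/11 = 27.3% (6.0 to 61.0) | 1.1 |
| 2 | 30.0% | 3/12 = 25.0% (5.5 to 57.2) | 1.2 |
| 4 | 30.0% | 3/14 = 21.4% (4.7 to 50.8) | 1.4 |

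**Step 5: late RC is a different case.** A patient with RC at 42 days or later does have pathology, so the direction is open. Suppose 2 such patients are added to 3/10. The rate becomes 3/12 = 25.0%, 4/12 = 33.3% or 5/12 = 41.7% if 0, 1 or 2 of them respond.

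**The case against.** The strongest defence is that 3.4 already fixes the denominator. A stated, response-evaluable set is a legitimate choice in a 10-patient tissue-based pilot, and no test or decision rule rests on this rate. That largely stands. It explains why 3.4 is the likelier reading and why the point is not an error in the primary analysis. It does not remove the contradictory general sentence in 10.2, or the one-directional effect of leaving out patients without RC.

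A reader might infer that the replacement rule hides the exclusion. The documents do not support that. Section 3.4 defines a safety set of all patients with at least one dose, 7.2.5 follows those without RC, and 10.2 promises a descriptive summary. If the treated number and the responder count are published, and the only exclusions are patients without RC, a reader can work out the all-treated rate.

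The count k is unknown and may be 0, since 4.1 requires patients to be eligible and willing for RC. This is correct, and in that case the two rates coincide.

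Counting every patient without RC as a non-responder gives a conservative lower figure, not an unbiased one, because surgery may be missed for reasons unrelated to response. Late pathology may also reflect other treatment, since 4.3 foresees alternative anticancer therapy. Both objections stand and shape the fix.

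**Conclusion.** The point holds as a conflict between 3.4 and 10.2 with a one-sided consequence on a secondary endpoint. If 3.4 governs, the reported rate equals the all-treated rate multiplied by (n + k)/n. With n = 10 that is a factor of 1.1, 1.2 or 1.4 for 1, 2 or 4 treated patients without RC, and 1.0 for none. The 3 responders, the n of exactly 10 and the values of k are assumptions. The intervals overlap widely, so no significant shift is claimed.

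A reader might go further and infer that the rate will be inflated against the historical controls in 1.7. That is not shown. Table 1 does not state whether its pT0 percentages are over all treated patients or only those who had surgery. It reports pT0 only, so it offers no comparator for downstaging to below pT2. Rounding does not settle the denominators either. In the phase II gemcitabine and cisplatin row, 26.7% fits no whole number over the listed 22 (5/22 = 22.7%, 6/22 = 27.3%) but does fit 4/15. That might hint at a subset, yet a percentage that does fit its listed n would not show that n counts everyone treated.

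**What to change.** - Reword 10.2 so that its sentence on patients not evaluable for the primary outcome refers to the endpoint-specific sets in 3.4, and say whether those patients enter the response rate and its interval.
- Report the pathologic response rate with an exact 95% CI for all patients with at least one dose, counting no RC as non-response and labelling it a conservative lower figure. Report the 3.4 rate beside it.
- Give the number of treated patients with no RC and the number with RC at 42 days or later.
- List late-RC pathology separately, noting any other anticancer therapy received before RC. Write down in advance how these patients count in the all-treated rate, so that they are not folded in without a rule.

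The cost is wording in two sections and a possibly lower reported rate. No extra visits or patients are needed, and treatment and surgical timing are unchanged.

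### Section 3.4 ties the 2-year DFS set to timely cystectomy and conflicts with 10.2; if 3.4 is followed, treated patients who fail before surgery leave the denominator

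*Protocol*

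**What the plan says.** Four places in the protocol bear on who counts for DFS.

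- **Section 3.4, DFS set.** A patient must "Meet evaluability criteria for complete response/partial response". That criterion is at least one dose of avelumab and "undergo RC < 42 days from last avelumab dose". The patient must also "participate in 90 day on study follow-up after RC and participate in off study follow-up as part of regular care up to 2 years post" (that is, after surgery).
- **Section 10.2.** Patients not evaluable for the primary outcome "will be considered evaluable for the safety analysis and secondary outcomes", but the same sentence limits them to a descriptive summary. DFS is estimated by Kaplan-Meier with a median and 95% confidence interval. No test against controls is planned.
- **Section 7.2.5.** After the 90-day safety period, "those patients who are evaluable for secondary endpoints will be followed off study for recurrence and survival for up to 2 years after RC". Treated patients without RC are followed for safety for 90 days after the end of their last cycle.
- **Section 1.7.** The hypothesis is that 2-year DFS will exceed that of historical controls without neoadjuvant chemotherapy and be similar to that of controls given cisplatin-based chemotherapy.

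**The concern.** Having RC, and having it in time, is decided after treatment starts and partly by how the disease behaves. A set conditioned on it is therefore selected on outcome. The clearest failure of a pre-operative treatment is progression or death that prevents surgery. Under 3.4 that patient is not counted as a DFS event and is not in the DFS set at all.

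Such failures are foreseeable. The study calendar puts surgery at days 41–64 and repeats chest and abdominal/pelvic imaging at the pre-surgery visit on days 40–50. Section 7.2.3 says imaging serves to detect progression. Section 3.4 also replaces patients who are not evaluable for the primary endpoint, so the target of 10 can be filled entirely with operated patients.

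The 42-day limit may matter for reading the surgical specimen. It has no evident purpose for DFS, because recurrence after a later RC can be observed in full.

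The historical comparison in 1.7 is at stake, and so is data collection. If 7.2.5 is read through 3.4, 2-year outcomes of the excluded patients may never be recorded, and no later analysis could restore them.

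**Working it through.** **The plan's own figures.** The only design calculation is the power of about 80% in section 10.1, for the T-cell endpoint. With n = 10, r = 0.5 and a 1 SD change, the SD of the difference is √(2(1 − 0.5)) = 1 SD, and the paired t-test at two-sided 5% has 80.3% power. That reproduces, but has no bearing on DFS. No DFS target, rate of missed or late RC, or dropout rate is stated.

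**Which patients each section includes.** The primary criteria in 3.4 require RC within 5 weeks (35 days) of the last dose and no systemic steroids above the stated threshold during treatment.

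| Patient with at least one dose | Primary set (3.4) | DFS set (3.4) | Secondary outcomes (10.2, literal) |
|---|---|---|---|
| RC within 35 days, steroids above threshold | no | yes* | yes, described |
| RC at 36–41 days | no | yes* | yes, described |
| RC at 42 days or later | no | **no** | yes, described |
| No RC (progression, death, other) | no | **no** | yes, described |

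*If the follow-up conditions are also met.

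The two sections can agree in the first two rows. In the last two they conflict. Even where 10.2 admits these patients, it does not say whether they enter the Kaplan-Meier estimate or are only listed beside it. Section 7.2.5 takes over the ambiguity, since its 2-year follow-up depends on who is evaluable for secondary endpoints.

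**Can the 42-day limit exclude someone operated on within the calendar?** Nominal dosing days are 1, 15 and 29, and RC is due by day 64.

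- Last dose day 29: 29 + 42 = day 71, after day 64, so RC by day 64 qualifies.
- Last dose day 15: 15 + 42 = day 57, so RC on days 57–64 does not qualify.
- Last dose day 1: 1 + 42 = day 43, so RC on days 43–64 does not qualify.

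A patient who stops avelumab early can thus have RC by day 64 and still fall outside the DFS set.

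**Illustration of size (assumed inputs).** Suppose 10 patients meet 3.4, 6 are disease-free at 2 years, and nobody is censored, so Kaplan-Meier equals the simple proportion. Add k treated patients whom 3.4 excludes and ignore the small shift in time origin.

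- All k have events, DFS = 6/(10 + k): k = 0, 60%; k = 1, 6/11 = 54.5%; k = 2, 6/12 = 50.0%; k = 3, 6/13 = 46.2%.
- The k patients have half the DFS of the others (30%), DFS = (6 + 0.3k)/(10 + k): 57.3%, 55.0% and 53.1% for k = 1, 2, 3.
- Over DFS of 50–80% in the 3.4 set and k = 1–3, all with events, the overstatement runs from 4.5 points (50% to 45.5%) to 18.5 points (80% to 61.5%).

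The exact 95% CI for 6/10 is 26% to 88%.

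**The case against.** The strongest reply is that exclusion is not established. Section 10.2 literally covers both groups, since no RC or late RC makes a patient inevaluable for the primary outcome. Section 3.1 speaks of following patients for 2 years without an evaluability limit. This stands in part: the bias depends on 3.4 being followed. But 10.2 does not settle the matter, because it offers only a descriptive summary and can be read as covering only patients who fail the primary criteria alone.

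Further points that stand:

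- DFS from RC is a legitimate measure if labelled as conditional on surgery. Straight-to-surgery controls may share that origin, but the documents do not say how they were timed. The cisplatin controls in 1.7 also had a pre-operative interval.
- With three doses given, RC at 42 days or later already breaches the day-64 limit, so that group should be small.
- The endpoint is secondary, in a 10-patient pilot, and its interval is far wider than the shift illustrated.

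Three stronger readings are tempting but unsupported:

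- A reader might infer that late RC certainly inflates DFS once excluded. Delay can have causes unrelated to disease, so the direction there is only likely.
- A reader might turn the median DFS range in 1.8 into a probability of losing a pre-RC failure. That needs a constant hazard from first dose and every early event preventing RC. The documents support neither.
- A reader might cite section 4.3, which says "Patients determined to be inevaluable will be removed from study". The group that 3.4 lists under inevaluable patients is those with less than one dose, so the sentence does not clearly reach treated patients without timely RC.

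**Conclusion.** The point holds as an inconsistency with a conditional bias. Section 3.4 defines the DFS set by timely RC, 10.2 points the other way without resolving it, and 7.2.5 leaves 2-year follow-up of the affected patients uncertain.

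If 3.4 governs, upward bias follows by construction for patients whose progression or death precludes RC. If no such patient occurs, their contribution is nil. The illustrated loss of about 5 points for one excluded failure and 10 for two rests on an assumed 60% and on those patients being events; it is not an estimate for this trial. Given the small sample and the descriptive role of DFS, this should be corrected but does not threaten the primary objective.

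**What to change.** - **Section 3.4:** define the 2-year DFS set as all patients with at least one dose. Count progression that precludes RC, or death before RC, as an event on its date. Remove the 42-day limit for DFS; it can stay for pathologic response. State the time origin, which must precede RC for these events to count; first dose is the natural choice.
- **Beside it:** report DFS measured from RC in operated patients, labelled as conditional on RC.
- **Section 7.2.5:** extend 2-year recurrence and survival follow-up to all treated patients, with a stated starting point for those without RC.
- **Section 10.2:** say that the Kaplan-Meier estimate uses this set, and clarify which patients are described only.

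The cost is wording in three sections, contacts about every 3 months for the few treated patients without timely RC, and a DFS figure that may be slightly less favourable. Treatment does not change.
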